8 STUDY ASSESSMENTS AND PROCEDURES

8.1 EFFICACY ASSESSMENTS

8.1.1 OXYGEN SATURATION

Continuous recording of O₂ saturation using the study pulse oximeter is planned for all infants through hospital discharge, **and for the sub-group of infants recruited at hospitals participating in home oximetry recording, will continue through 43 weeks + 6 days PMA (i.e. one week following the last dose of study drug).** The study oximeter will be the Masimo RAD-97, set at the minimum possible averaging time of 2–4 sec and a sampling rate of 1 sec (high resolution). The oximeter will be preset in the sleep lab mode, hence with no “probe off,” “low battery,” or physiologic visual displays or alarms. The internal data storage capacity of the RAD-97 oximeter is sufficient for 28 days of continuous data collection.

Inpatient Phase: During the inpatient phase, the RAD-97 will be a 2nd oximeter, in addition to the one used for standard monitoring in the NICU. Continuous oximeter recordings will be obtained whenever in the NICU. Data will be downloaded from the monitor, and archived by the DCC, at least every 4 weeks while in the NICU and at discharge.

Please note: Some sites may discontinue oximeter recordings at hospital discharge.

Outpatient Phase: **At sites participating in the home oximetry portion of the study,** prior to discharge, the family will be trained in the use of the RAD-97, and will be asked to use the oximeter during all sleep times and quiet awake periods until 43 weeks + 6 days PMA. At home, therefore, we expect at least 8 – 12 hours of use per day, so the memory capacity of the RAD-97 should be sufficient to complete the outpatient phase.

Following discharge, the family will be contacted within the first 2 – 3 days, and then at least weekly to provide support in the use of the study monitor and to support other aspects of the study protocol. As part of their support of the use the monitor at home, study site staff will assess if the use pattern is such that the oximeter memory might be close to capacity, and determine if it is necessary to schedule an additional data download.

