8.3.2 DEFINITION OF SERIOUS ADVERSE EVENTS (SAE)

An adverse event (AE) or suspected adverse reaction is considered "serious" if, in the view of either the investigator or sponsor, it results in any of the following outcomes: death, a life-threatening adverse event, inpatient hospitalization or prolongation of existing hospitalization, or a persistent or significant incapacity or substantial disruption of the ability to conduct normal life functions. Important medical events that may not result in death, be life-threatening, or require hospitalization may be considered

serious when, based upon appropriate medical judgment, they may jeopardize the participant and may require medical or surgical intervention to prevent one of the outcomes listed in this definition.

Note that for the purpose of this study, delaying discharge of an infant related to achieving a specified 'spell-free' number of days shall NOT be considered a 'prolongation of existing hospitalization' for the purpose of categorizing an event as a serious adverse event.

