9.2 SAMPLE SIZE DETERMINATION

Sample Size: We will randomize 220 infants, **110 in each treatment group**, with ≥ 100 infants/group available for final analyses. Sample size considerations focus on PMA week-specific differences between the extended caffeine vs. placebo infants for our primary outcome of #sec/day $< 90\%$ saturation from 36 to 42 weeks PMA. Preliminary data showed effect sizes at 37 and 38 weeks PMA of 0.87 and 0.73. With the decline in **IH** with increasing age, we expect that 1) the caffeine effect may decline and 2) moderate effects will be needed to achieve a meaningful reduction in **IH** to 42 weeks PMA. Therefore, we consider an effect size of 0.50 to represent a meaningful detectable difference between groups. Final samples of $n=100$ per group gives 82% power to detect this effect, testing at the overall 2-tailed .05 level with a familywise Type I error correction adjusting for multiple testing across weeks. Secondary outcomes of **#IH** events and **#sec < 80% saturation/day** showed effect sizes at 38 weeks PMA of 0.73 and 0.46 in our pilot data.

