9.4 STATISTICAL ANALYSES

9.4.1 GENERAL APPROACH

Statistical significance will be declared at the two-sided $p < 0.05$ level; when appropriate, correction for multiple comparisons will be employed. For analyses of primary and secondary objectives, we will adjust for demographic and clinical differences. When employed, tests for interaction will at the 0.1 alpha level. Results will be presented through measures of effect and 95% confidence intervals. If lost to follow-up exceeds the 10% anticipated under sample size considerations, multiple imputation on the intent-to-treat population will be used for sensitivity analyses that account for missing data. All computations will be performed using the latest available version of SAS®.

Demographic variables and subject characteristics will be summarized descriptively by treatment assignment and overall. Continuous parameters will be summarized using descriptive statistics (N, mean, median, standard deviation, minimum and maximum value). Categorical demographic parameters, such as gender, will be summarized as a percentage of the population.

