will be determined for each infant, confirmed in our pilot study to be $\geq 95\%$ for the PMA weeks being studied. An **IH** event is defined as SaO_2 decrease $\geq 10\%$ (event threshold) and lasting ≥ 5 sec; the event ends when SaO_2 increases above the event threshold. For sec of SaO_2 below threshold, all sec below the threshold are included. We will compare extended caffeine vs. placebo infants on measures of **IH**, with # of sec $< 90\%$ saturation/day our primary outcome. Our pilot data showed that # of sec $< 90\%$ optimally discriminates between infants on vs. not on extended caffeine, with high correlation between #sec $< 90\%$ saturation/day and multiple other measures to quantify **IH** which will be secondary outcomes, including #**IH** events/day, # sec $< 80\%$ saturation/day, nadir saturation during events, duration of events (Spearman's correlations $r > 0.90$, and AOC during events below 90% and 80% threshold saturation ($r=0.83$).⁹⁰ Preliminary data showed that these outcomes follow a log-normal distribution, and data will be log-transformed for analysis; non-parametric procedures will be considered as an alternative analytic approach if warranted by the distribution of the **IH** outcomes. Exploratory analyses will also compare caffeine vs. placebo on heart rate data. As a check on randomization, preliminary analyses will compare the two study groups on key characteristics including gestational age, birth weight, infant sex, morbidity (e.g., necrotizing enterocolitis, mild BPD), and severity of illness measures; variables found to differ meaningfully between groups will be controlled for in primary analyses through multiple linear regression models. Primary analyses will determine how long extended caffeine provides an advantage over placebo by testing PMA week-specific differences between study groups through multiple regression models controlling for key covariates using Holm's family-wise error adjustment to account for multiple testing across PMA weeks.

Primary Objective 2: Compare changes in a panel of inflammation-related cytokines and chemokines, from enrollment to the target age of 38 weeks + 0 days PMA, in infants randomized to extended caffeine treatment to infants assigned to receive placebo.

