Primary neuroimaging outcome measures will include microstructural measures derived from our DTI analyses (FA/MD) and proton MRS. Secondary outcomes will include regional tissue volumes. Individual end-of-study MRI parameters will be compared through analysis of covariance multiple linear regression models controlling for the MRI parameter at baseline along with key covariates including indicators of comorbidities potentially associated with brain development, using the Benjamini and Hochberg method to account for multiple testing by controlling the false discovery rate. .

Secondary Objective 1: Examine the association between salivary caffeine concentrations and **IH** outcomes at the one week post randomization and 40 weeks + 0 days PMA assessments.

Analyses will examine the association between salivary caffeine levels and **IH** outcomes, both at the end of the inpatient stay and at study completion. Caffeine levels at home will also be used to verify protocol adherence. Secondary analyses will also include relationship between individual neonatal morbidities and extent of **IH** in caffeine and placebo groups. Exploratory analyses will model the trends in **IH** parameters over time in the extended caffeine and placebo groups using mixed-effects linear regression models for longitudinal data. Should missing data become a problem, multiple imputation methods will be used to account for potential bias in the complete case analysis.

Secondary Objective 2: Determine whether changes, from baseline to follow-up, in inflammatory or MRI biomarkers are mediated by caffeine-related reduced **IH**.

We will also examine **IH** levels during the study period as a mediator of the extended caffeine effect. Initial analyses will examine associations between **IH** parameters and inflammatory biomarkers, to determine which **IH** measures are most strongly correlated with inflammation at study completion. Linear structural equation mediational models will be used to determine whether any associations between extended caffeine treatment and changes in inflammatory biomarkers can be explained by **IH** parameters during the study period. The relationship between neonatal morbidities, Inflammation, and response to caffeine will also be assessed.

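### The weekly primary tests for Objective 1 use only infants recorded that week; a repeated-measures model would recover precision lost to discharge at sites without home oximetry

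*Combined protocol and SAP*

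**What the plan says.** **Primary model.** Section 9.4.2 answers the duration-of-benefit question by "testing PMA week-specific differences between study groups through multiple regression models controlling for key covariates", with Holm's adjustment across weeks. An infant qualifies with 10 hours of acceptable recording in any one PMA week. No rule covers the weeks in which that infant has no recording.

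**Recording.** Section 8.1.1 plans oximetry for every infant only up to discharge, and notes: "Some sites may discontinue oximeter recordings at hospital discharge". Section 6.5.1 agrees. Section 1.1 (Participant Duration) puts most discharges at 34 to 40 weeks PMA. The amendment history (4.1 to 4.2) accepts home data on only part of the sample.

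**Longitudinal model.** The only one planned is exploratory, under Secondary Objective 1. It would model trends in IH "parameters over time in the extended caffeine and placebo groups using mixed-effects linear regression models for longitudinal data".

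**Missing data.** Section 9.4.1 offers multiple imputation as a sensitivity analysis: "If lost to follow-up exceeds the 10% anticipated under sample size considerations". Section 7.3 defines loss to follow-up by the end-of-study visit and failure of contact. A second clause, under Secondary Objective 1 in section 9.4.2, allows imputation if missing data become a problem, and describes the default as complete case.

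**Power.** Section 9.2 states: "Final samples of $n=100$ per group gives 82% power to detect this effect", with "testing at the overall 2-tailed .05 level with a familywise Type I error correction adjusting for multiple testing across weeks". The effect is set as follows: "we consider an effect size of 0.50 to represent a meaningful detectable difference between groups".

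**The concern.** The hypothesis is that the effect lasts through 42 weeks PMA, so the late weeks carry the answer. At a site without home oximetry, the infants recorded in those weeks are the ones not yet discharged. That is a status reached after randomization. The note in section 8.3.2 on "delaying discharge of an infant related to achieving a specified" spell-free interval shows that respiratory events can hold up discharge.

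Two things follow. First, the late-week samples shrink, while the power statement assumes 100 per group in each week tested. Second, a week-specific regression cannot use what was recorded for the same infant in earlier weeks. Those earlier values do enter the earlier weeks' tests; they simply contribute nothing to weeks 40 to 42. An infant's own earlier IH is likely to predict later IH, so precision is given up in the weeks where it is scarcest.

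**Working it through.** **Inputs from the documents:** 100 per group, effect 0.50 SD, two-sided 0.05 overall, weeks 36 to 42 (read as seven tests), Holm (all from 9.2 and 9.4.2).

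**Inputs not in the documents, therefore assumed:** the share of infants at home-oximetry sites, the discharge distribution beyond the 34-to-40-week range, the between-week correlation, and the link between IH and discharge.

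**1. Reproduce 82%.** With n per group, power is about Φ(0.50·√(n/2) − z), where z = 2.690 for alpha 0.05/7 (Bonferroni, and Holm's first step). For n = 100: 0.50·√50 = 3.536; 3.536 − 2.690 = 0.846; power 80.1% (79.2% by noncentral t). Six tests give 81.5% and five give 83.1%. The number of tests behind 82% is not stated, but the figure is reproduced to within two points, and only with about 100 infants per group in the week tested.

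**2. Power with fewer infants that week** (same effect and alpha, normal approximation):

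| n per group | 100 | 80 | 60 | 50 | 40 | 30 |
|---|---|---|---|---|---|---|
| Power | 80.1% | 68.2% | 51.9% | 42.5% | 32.5% | 22.6% |

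The effect detectable with 80% power goes from 0.50 SD at n = 100 to 0.71 at 50 and 0.91 at 30.

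**3. What earlier weeks add.** Suppose n1 per group are seen early and n2 of them in the late week, with correlation ρ. The late-week variance, in units of the outcome variance, is (1 − ρ²)/n2 + ρ²/n1, and its reciprocal is the effective n. Example: ρ = 0.5, n1 = 100, n2 = 50 gives 0.75/50 + 0.25/100 = 0.0175, so 57.1. Power is by noncentral t, which is why the n2 = 50 baseline reads 40.7% here and 42.5% in step 2.

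| n2 | Power, that week alone | ρ = 0.5: effective n, power | ρ = 0.8: effective n, power |
|---|---|---|---|
| 25 | 16.2% | 30.8, 21.5% | 48.1, 38.8% |
| 50 | 40.7% | 57.1, 47.6% | 73.5, 61.9% |
| 75 | 63.1% | 80.0, 66.9% | 89.3, 73.1% |

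For n2 = 50, ρ = 0.6 and 0.7 give 61.0 (51.2%) and 66.2 (55.8%).

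**4. Simulation of the whole sequence.** Assumptions: 100 per arm, true effect −0.50 SD every week, between-week correlation 0.6 treated as known, weekly discharge probability rising from 0.15 to 0.60, discharge less likely after a week of high IH, alpha 0.05/7. Week 42:

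| Share at home sites | n per arm | Separate regressions | Mixed model |
|---|---|---|---|
| 25% | 29 | power 0.20, estimate −0.53 | power 0.34, estimate −0.48 |
| 50% | 53 | power 0.43, estimate −0.50 | power 0.55, estimate −0.48 |
| 75% | 77 | power 0.67, estimate −0.51 | power 0.72, estimate −0.50 |

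If the true effect fades to zero by weeks 41 and 42, separate regressions show −0.05 SD (25% home) or −0.02 SD (50% home); the mixed model shows about 0.00 to 0.01. When discharge was instead made to depend on unobserved IH, the largest late-week departure was 0.06 SD (−0.56 against −0.50, 25% home).

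**5. Holm beyond its first step.** Alpha 0.05/7 is conservative when several weeks carry an effect. With full Holm, all weeks at 0.50, correlation 0.6 and separate regressions, per-week power is about 88% at 100 per arm throughout. With discharge unrelated to IH, week 42 falls to 61% when 52 per arm remain (50% home) and 35% when 28 remain (25% home). The loss remains.

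**The case against.** **Bias.** A reader might infer that selection by discharge seriously distorts the primary result. The documents do not support that. They describe this IH as clinically inapparent (2.1), the study oximeter shows no values and sounds no alarms, and clinical staff are blinded (6.3, 8.1.1). The section 8.3.2 note concerns spells, not recorded seconds below 90%. Any correlation between discharge and the outcome is assumed, and even with one assumed the pooled contrast moved little. This part of the objection stands.

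**Imputation.** A reader might also infer that the plan makes no provision for unrecorded weeks. It has the second clause in section 9.4.2. That clause has no threshold and no model, and it sits under a secondary objective, so it does not settle how the primary test handles these infants.

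**The gain rests on unstated inputs.** This stands. The home-site share is not given. Randomization runs to 36 weeks + 6 days while discharge can begin at 34 weeks, so no single early week is sure to have 100 per group. With 75% at home sites the simulated gain is only five points.

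**The planned mixed model cannot simply be promoted.** Also true: it is an exploratory model of trends, so a primary version must be written afresh. Separate regressions are themselves an inference from week-specific tests with Holm, but the natural one.

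**Conclusion.** A cheap improvement, not a flaw that invalidates the trial. As written, each late-week test loses the discharged infants of non-home sites and ignores what was recorded for them earlier, and neither imputation clause defines what to do.

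The main consequence is precision. With 50 per group at week 40 and a correlation of 0.5 to 0.8, power in that week goes from 41% to 48-62%. It improved in every scenario tested, less so when most infants are at home sites, and never reached 82% in the late weeks. Bias in the pooled weekly contrast was about 0.00 to 0.05 SD, 0.06 at most, under assumed mechanisms. It could be larger if caffeine itself changes the timing of discharge, on which the documents give no data.

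**What to change.** Before unblinding, amend section 9.4.2 as follows.

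- **Primary analysis:** a repeated-measures mixed model of log seconds below 90%, with PMA week as a category, treatment-by-week, the covariates already named, and site or home-oximetry status. Use an unstructured within-infant covariance with a simpler prespecified fallback, since weeks 36 to 42 alone need 7 × 8 / 2 = 28 parameters. Allow for clustering, because multiples are randomized together (4.1, 6.3). Take the Holm-adjusted weekly contrasts from this model.
- **Sensitivity analyses:** repeat weeks 38 to 42 at home-oximetry sites only. Allocation is stratified by site, so the arms there remain as randomized, though recordings can still be missing through family non-use. Add one missing-not-at-random analysis.
- **Imputation:** tie the trigger to missing infant-weeks instead of loss to follow-up.
- **Reporting:** give infants per arm per week, and recompute power in section 9.2 from the expected weekly numbers.

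The cost is SAP wording and modest programming, with no new data. The downside is reliance on missing at random: no post-discharge recordings exist at non-home sites, so estimates for those infants borrow from their earlier weeks and from home sites.

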Study Duration:	Enrollment is scheduled to start in December, 2018 and will continue at least through May of 2022, with completion of follow-up and data analyses thereafter.

Participant Duration: The maximum time between study enrollment to study completion for an individual participant would be 15 weeks if enrollment was as early as 32 weeks + 0 days and the final visit was at the latest time permitted at 46 weeks + 6 days. Since enrollment is permitted as late as 36 weeks + 6 days, and the final study visit may occur as early as 43 weeks + 6 days, a participant may complete the full study in as few as 7 weeks.

[figure not shown]
Hospital discharge most commonly occurs between 34 and 40 weeks PMA, and we expect most infants to have roughly half their time in the study as in-patient and half as outpatient, though this may be vary widely.

The end of study procedures include: return of the oximeter (if applicable), salivary sample and any unused study drug. As noted above, these procedures will be done at the convenience of the family, and although a face-to-visit is preferred, all items may be shipped back if, for any reason, the parents prefer not to travel to the site.

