1.3 SCHEDULE OF ACTIVITIES (SOA)

Study Procedures	≤30 weeks + 6 days thru 36 weeks + 6 days	32 weeks + 0 days thru 36 weeks + 6 days	Target: 1 day post last routine caffeine dose (but window of up to 3 calendar days allowed)	1 week on study drug (up to 14 days post 1 st dose)	36 weeks + 0 days PMA	Hospital Discharge	40 weeks + 0 days PMA	42 weeks + 6 days PMA	43 weeks + 6 Days PMA
Screening	X								
Informed Consent		X							
Enrollment		X							
Baseline Data Collection		X							
Pulse oximetry recording						X ¹⁰			
Randomization			X						
Once daily study drug				X ¹					
Twice daily study drug							X ¹		
Drug log						X			
Saliva for caffeine level				X			X ²		
Biomarker blood sample		X ³				X ³			
MRI/MRS		X ⁴							X ⁴
Pre-discharge checklist						X ⁵			
Weekly parent phone contact							X ⁶		
Infant sleep Q								X ⁷	
End of study visit									X ⁸
Concomitant medications					X ⁹				
Adverse Event					X ⁹				

1. Study drug (caffeine base 5 mg/kg QD or placebo, weight adjusted weekly while in hospital) begins 1 day after last day of routine caffeine, but no later than the 3rd calendar day after last dose of routine caffeine. Dose is increased to 5 mg/kg BID at 36 + 0; finally, the last dose of study drug is at 42 + 6. Note that initial dose will be BID if enrolled at 36 + 0 or later.
2. 2nd caffeine level targeted at 40 + 0, (no earlier than 39 + 0 and no later than last day of study drug), whether in hospital or at home.
3. 1st biomarker blood sample should be obtained as close as possible to the day of randomization. Whenever possible, this blood sample should be timed with a clinically required blood draw. To facilitate obtaining this sample at the time of a clinical blood draw, this sample may be obtained at any time after consent, but no later than the 2nd calendar day after the first dose of study drug. The 2nd sample is to be obtained at 38 + 0 (+ or - 3 days) or within 2 calendar days prior to hospital discharge, whichever comes first.
4. 1st MRI/MRS is done in hospital sometime between enrollment and 3 calendar days after starting study drug. 2nd MRI/MRS is targeted at 43 + 0 but should be no later than 46 + 6. MRI visit may be combined with the end of study visit. MRI/MRS scans will only be performed for subjects enrolled at sites participating in the MRI/MRS portion of the study.

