3 OBJECTIVES AND ENDPOINTS

OBJECTIVES	ENDPOINTS	JUSTIFICATION FOR ENDPOINTS
Primary		

Primary Objective 1: Compare the extent of IH exposure, from randomization through 42 weeks + 6 days PMA (within each gestational week and overall), in infants randomized to extended caffeine treatment to infants assigned to receive placebo.
 
Primary Objective 2: Compare changes in a panel of inflammation-related cytokines and chemokines, from enrollment to the target age of 38 weeks + 0 days PMA, in infants randomized to extended caffeine treatment to infants assigned to receive placebo.
 
Primary Objective 3: Compare changes in quantitative MRI structural, microstructural and metabolic biomarkers of acute injury, from enrollment to 43-46 weeks PMA, in infants randomized to extended caffeine treatment to infants assigned to receive placebo.
	
# of sec of IH <90% at each PMA week
 
Change in plasma concentration of each inflammatory biomarker from baseline to 38 weeks PMA.
 
Difference between neuroimaging measures at baseline and at 43-46 weeks PMA, including diffusion tensor imaging (DTI) and proton magnetic resonance spectroscopy (MRS).
	
# of sec of IH <90% the most representative measure to quantitate extent of IH
 
Measuring biomarker concentrations at 38 weeks will be a sufficient interval for changes since baseline, and will be the interval during which differences in extent of IH will be maximal.
 
Quantitative MRI is a sensitive modality for assessing structural, biochemical, and functional changes consequent to IH and extent of improvement with extended caffeine treatment. Assessing at study end will provide maximal time for adverse MRI changes consequent to IH since starting study drug.

Secondary		

Secondary Objective 1: Examine the association between salivary caffeine concentrations and IH outcomes at the one week post randomization and 40 weeks + 0 days PMA assessments.
 
Secondary Objective 2: Determine whether changes, from baseline to follow-up, in
	
Extent of IH (# of sec <90%) paired with saliva caffeine level during PMA week of oximetry recording.
 
Change in plasma concentration for each inflammatory
	
# of sec of IH <90% is the most representative measure of extent of IH during the week corresponding in time to the caffeine level.
 
See above

OBJECTIVES	ENDPOINTS	JUSTIFICATION FOR ENDPOINTS

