inflammatory or MRI biomarkers are mediated by caffeine-related reduced IH .	biomarker, from baseline to 38 weeks PMA, in relation to IH measures. Change in each MRI parameter, from baseline to 43-46 weeks PMA in relation to IH measures.	

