Analyses for this objective will be performed on the mITT population and compare those randomized to extended caffeine vs. placebo. To be included in the analyses a subject must have had a baseline/follow-up pair of blood samples for which at least one biomarker was measured on both samples. Analysis will focus on change in inflammatory biomarker levels over the study period. Preliminary analyses will examine the distribution of biomarkers, and data will be transformed (e.g., logged) as appropriate for analysis. Two approaches will be taken for the primary analyses, comparing changes in biomarkers over the study period in extended caffeine vs. placebo infants. First, we will conduct separate analyses of each inflammatory biomarker using linear regression models to compare study groups at study completion, controlling for baseline levels as well as key covariates including morbidities that might be associated with inflammation, using the Benjamini and Hochberg method to account for multiple testing by controlling the false discovery rate. Second, we will examine the structure of the biomarker data using data reduction procedures of factor analyses (identifying latent variables reflected by the set of biomarkers) and latent profile analysis (identifying subgroups of infants with similar patterns of biomarker profiles). Extended caffeine vs. placebo infants would then be compared on the summary measures of inflammation biomarkers resulting from these analyses.

Primary Objective 3: Compare changes in quantitative MRI structural, microstructural and metabolic biomarkers of acute injury, from enrollment to 43-46 weeks PMA, in infants randomized to extended caffeine treatment to infants assigned to receive placebo.

Analyses for this objective will be performed on the mITT population and compare those randomized to extended caffeine vs. placebo. To be included in the analyses a subject must have had a baseline/follow-up pair of MRI studies completed from which at least one MRI endpoint could be measured on both assessments.

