Similarly we will also examine associations between changes in MRI parameters and levels of **IH** during the study period through correlation and linear regression models with the goal of determining **IH** parameters most strongly associated with brain injury. Structural equation mediational models will determine whether any associations between extended caffeine and MRI changes can be explained by the level of **IH** activity during the study.

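### Secondary Objective 2 does not say that the IH window for the inflammation mediator ends at the second blood sample, and it searches for the best-correlated IH measures without naming a primary mediator

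*Combined protocol and SAP*

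**What the plan says.** **Window.** Section 9.4.2, Secondary Objective 2, examines IH "levels during the study period as a mediator of the extended caffeine effect". It gives no start or end date. The outcome is dated: in the Section 3 table it is the change in each biomarker "from baseline to 38 weeks PMA, in relation to IH measures". The second sample is due at 38+0 ± 3 days "or within 2 calendar days prior to hospital discharge, whichever comes first" (Section 1.3, footnote 3). Recording continues beyond that sample for two groups:

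- infants at home-oximetry sites, to 43+6 (Section 8.1.1);
- infants still in hospital. Section 1.1 says "Hospital discharge most commonly occurs between 34 and 40 weeks PMA".

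For Primary Objective 1, IH is analysed from randomization to 42+6 (Sections 9.1 and 9.4.2).

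**Measure.** Initial analyses are to find which IH "measures are most strongly correlated with inflammation at study completion"; structural-equation mediation models follow. For MRI, changes are related to IH "during the study period through correlation and linear regression models with the goal of determining" the IH parameters tied most closely to brain injury, again followed by mediation models. Seconds below 90% saturation is the named IH outcome for Primary Objective 1 and Secondary Objective 1. Secondary Objective 2 refers only to IH measures or parameters. No hold-out sample, data split or correction for the search is described.

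**The concern.** A mediator has to precede its outcome. IH recorded after the second blood sample cannot have caused the biomarker change measured at that sample. If it is averaged in and caffeine's effect on IH weakens with age, the indirect effect is computed from a diluted caffeine-to-IH difference and mediation is understated. Section 9.2 says the effect may decline.

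Choosing the mediator by its correlation with the outcome, then testing it on the same infants, makes the IH-to-outcome path look stronger than it is.

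Mediation by reduced IH is the whole of Secondary Objective 2 and part of Hypotheses 2 and 3 (Section 4.1). What is at stake is the mechanistic claim. The randomized comparisons do not depend on it.

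**Working it through.** The plan gives no power or error figure for Secondary Objective 2, so there is none to reproduce. The sizes below are illustrations on stated assumptions.

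**1. How much recording can follow the sample.** Take a 34+0 start and a 38+0 sample. PMA weeks 34–37 give 28 days before the sample; weeks 38–42 give 35 days after it at a home-oximetry site, to 42+6. An infant discharged at 40+0 has 14 days after a 38+0 sample, or 17 after one at 37+4, even at an inpatient-only site.

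**2. Effect of the window.** Assume the outcome depends only on mean pre-sample IH, P, and that true mediation is 100%. Let U be the hours-weighted mean IH over the window used. Then

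estimated proportion mediated = (mean caffeine effect in window used ÷ mean effect before sample) × Cov(P,U) ÷ Var(U).

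Inputs:
- Effect 0.87 SD to week 37, then falling 0.14 per week. Section 9.2 gives 0.87 and 0.73 at weeks 37 and 38; the rest is extrapolated.
- Recording 24 h/day before the sample and 8–12 h/day at home (Section 8.1.1 expects at least 8–12).
- Residual weekly IH with SD 1 and either exchangeable correlation 0.6 or AR(1) 0.8 (assumed).

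Worked case, 10 h/day at home, exchangeable 0.6:
- Hours: 28 × 24 = 672 before, 35 × 10 = 350 after; pre-sample weight 672/1,022 = 0.6575.
- Effects in weeks 38–42: 0.73, 0.59, 0.45, 0.31, 0.17; mean 0.45.
- Mean effect used: 0.6575 × 0.87 + 0.3425 × 0.45 = 0.726; ratio 0.726/0.87 = 0.835.
- Variances of the 4-week and 5-week means: 0.70 and 0.68; covariance 0.60.
- Cov(P,U) = 0.6575 × 0.70 + 0.3425 × 0.60 = 0.666.
- Var(U) = 0.6575² × 0.70 + 2 × 0.6575 × 0.3425 × 0.60 + 0.3425² × 0.68 = 0.653.
- Proportion: 0.835 × 0.666/0.653 = 0.85.

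Ranges over hours, correlation structure and a variant with the effect floored at 0.50:

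| Case | Declining effect | Constant effect |
|---|---|---|
| All infants with home oximetry | 0.83–0.97 | 1.02–1.08 |
| Home share 75% (assumed) | 0.87–0.98 | no understatement |
| Home share 50% (assumed) | 0.92–0.98 | no understatement |
| Home share 25% (assumed) | 0.96–0.99 | no understatement |
| Inpatient only, discharged 40+0 | 0.92–0.94 | 1.00–1.02 |

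The inpatient row: (4 × 0.87 + 0.73 + 0.59)/6 = 0.80; 0.80/0.87 = 0.92, times 1.00 (exchangeable) or 1.02 (AR(1)).

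Harsher assumptions give more. With only 45% of the mediator's weight before the sample, and an abrupt fall from 0.8 SD to 0.2–0.5 SD, the estimate is about 0.55–0.80.

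**3. Effect of the search.** Simulation: 200 infants (100 per arm, Section 9.2), 20,000 replicates, and the seven IH measures of Section 9.4.2 (seconds below 90%, events, seconds below 80%, nadir, duration, area below 90% and below 80%). Caffeine effect on IH 0.6 SD (assumed), no IH-to-biomarker effect, the top-correlated measure carried forward, the path tested at 5% adjusting for arm. The pilot correlations with seconds below 90% are above 0.90, or 0.83 for area. False mediation means that caffeine–IH, IH–biomarker and caffeine–biomarker are all significant.

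| Correlation among measures | Path error, no direct effect | False mediation, no direct effect | False mediation, 0.5 SD direct effect |
|---|---|---|---|
| 0.95 | 9.2% | 0.5% | 8.3% |
| 0.90 | 11.4% | 0.6% | 9.7% |
| 0.83 | 13.9% | 0.7% | 12.0% |
| Linked only through seconds below 90% | 14.7% | 0.7% | 11.9% |

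With seconds below 90% named in advance, the path error is 4.9–5.2%, and false mediation with a 0.5 SD direct effect is about 5%.

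**The case against.** **The shorter window is probably what was meant.** Under Primary Objective 2 the same section says "Analysis will focus on change in inflammatory biomarker levels over the study period", although the last blood sample is at about 38 weeks, so the study period there can only be the interval between samples. Hypothesis 2 dates inflammation to 37–38 weeks. In Section 3 the Secondary Objective 2 row refers back for its justification, plausibly to the statement that the interval to 38 weeks "will be the interval during which differences in extent of IH will be maximal". This stands as evidence of intent. It does not fix the analysis: no passage closes the IH window at the sample, and the section uses its terms loosely. Under Secondary Objective 1, study completion is set against the end of the inpatient stay; for inflammation it must mean a sample drawn at or before discharge.

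**Stronger readings the documents do not support.**
- A reader might infer that the plan defines the mediator window as ending at 43+6. That date is attached to the study period only in Section 6.3, in a sentence on oximeter displays and alarms.
- A reader might infer that the plan's false-mediation rate is 9–14%. That is the error of one path, and only if the single top measure is carried forward. The plan speaks of measures and parameters in the plural, so top-one selection is implied, not stated. It fits mediation models to explain any associations with caffeine; under that condition, with no such association, false mediation is below 1% per biomarker.
- A reader might expect post-sample IH to create spurious mediation because inflammation drives later IH. The documents give no basis for sizing such a path.
- The timing point does not carry over to MRI: the second scan is targeted at 43+0, after an IH window ending at 42+6.

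**The sizes rest on assumptions.** The decline extrapolates two pilot values, the home-oximetry share is not given, and the model assumes pre-sample IH is measured without error. The noise of a short window is therefore not weighed against the bias removed. This is a fair limit.

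**Existing multiplicity language.** Section 9.4.1 promises correction where appropriate, and Benjamini–Hochberg is specified for the group comparisons. Neither is applied to this search.

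**Conclusion.** The point holds as a gap in specification for a secondary, mechanistic objective. Followed literally, the text admits post-outcome IH for home-oximetry infants and for those still in hospital after the sample. It also searches by correlation with the outcome, apparently on the same infants, without naming a mediator or labelling the search exploratory.

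The consequence is modest. Mediation is understated only if the caffeine effect on IH declines with age, and on the main assumptions full mediation would still be estimated at 0.83 or more. Selection raises the path error to about 9–14% (14.7% in the loosest structure) only under top-one selection. It matters mainly when caffeine changes the biomarker by another route: with an assumed 0.5 SD direct effect, false mediation is about 8–12% against about 5%. Section 2.2 does propose a second caffeine mechanism, but in the brain rather than in plasma biomarkers.

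The primary comparisons and the sample size are unaffected. It is worth settling before unblinding because the change is nearly free.

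**What to change.** Add to Secondary Objective 2:

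1. The inflammation mediator is log(seconds below 90% per 24 h of recorded data), from the later of first study-drug dose and baseline blood sample to that infant's second blood sample. The start needs this wording because the baseline sample may be drawn up to the second calendar day after first dose.
2. Seconds below 90% is the pre-specified mediator for both biomarkers and MRI. The search across other IH measures is exploratory.
3. For MRI, use recording up to 42+6 and never after the infant's second scan, with a sensitivity analysis restricted to inpatient recording, which all sites have.
4. Report the length of each infant's biomarker window, and add a sensitivity analysis requiring a minimum amount of recording, for example the 10 hours already used for Primary Objective 1.

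The cost is a few sentences; sample dates and continuous recordings are already collected, and nothing changes for infants or sites. The downside is a window that varies with start and discharge and can be short. From first dose it is 42 days for a 32+0 start and 38+0 sample, 8 days for a 36+6 start and 38+0 sample, and 5 days if that sample is at 37+4. It is up to 2 days less if the baseline sample follows the first dose, and less again with earlier discharge.
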